2.3.2 Background on MGD014

MGD014 (HIV_{A32} x CD3) is an HIV-1 env x CD3 DART molecule. MGD014 is designed to target HIV-1-infected, env-expressing cells for recognition and elimination by CD3-expressing T lymphocytes as effector cells. The anti-HIV-1 env component of MGD014 is derived from A32, a non-neutralizing mAb that recognizes highly conserved regions (C1-C2) of the gp120 subunit of HIV-1 env and is broadly reactive with env from diverse isolates of HIV-1. The 24

HIV-1 env residues that comprise the conformational epitope plus 12 accessory residues that may influence binding to the A32 epitope are conserved at an average frequency of 99.0% (range: 95.2-99.9%) across all HIV-1 subtypes (based on analysis of 5923 HIV-1 env sequences in the Los Alamos National Laboratory database). The anti-human CD3 component of MGD014 is derived from mAb hXR32, which is cross-reactive with similar affinity to cynomolgus or rhesus monkey CD3. To prolong circulating half-life, MGD014 contains a human IgG1 Fc domain that has been mutated to greatly reduce or eliminate effector function via binding to Fc γ Rs and complement, while retaining binding to the neonatal Fc receptor to take advantage of the IgG salvage pathway mediated by this receptor.

A schematic depicting MGD014 DART molecule structure and mechanism of action is shown in **Figure 1**. Refer to the **MGD014 IB** for additional information.

2.3.2.1 MGD014 Clinical Experience

One clinical study of MGD014, Study CP-MGD014-01, is complete. This trial was a Phase 1, open-label, single-center study to evaluate the safety, immunologic, and virologic responses of MGD014. Refer to the **MGD014 IB** for additional information.

As of 26 September 2020, Study CP-MGD014-01 enrolled 21 PWH on ART and dosed with single-dose MGD014 as follows: 1 participant each at 0.1 and 0.3 mcg/kg; 4 participants at 1 mcg/kg; and 3 participants each at 3, 10, 30, 100, and 300 mcg/kg MGD014.

Treatment-related AEs were reported among 4 of 21 (19.0%) participants receiving MGD014. These included AEs of feeling hot (n = 1 at 3.0 mcg/kg), diarrhea (n = 1 at 10 mcg/kg), flushing (n = 1 at 100 mcg/kg), and electrocardiogram QT prolonged and sensory disturbance (both in the same participant at 100 mcg/kg). All AEs were Grade 1 in severity, possibly related to MGD014, and occurred on the day of study drug infusion. All treatment-related AEs resolved without intervention. No dose-limiting toxicity (DLT), serious adverse events (SAEs), deaths, or treatment-related AEs leading to study drug discontinuation were reported.

Eighteen participants were evaluable for preliminary PK analysis following single administration of 0.1, 0.3, 1, 3, 10, 30, or 100 mcg/kg of MGD014. Dose normalized values of C_{max} and area under the concentration-time curve from time zero to infinity (AUC_{0-inf}) are approximately constant for the 3 to 100 mcg/kg doses, indicating dose proportionality in MGD014 PK for this dose range. Estimates for $t_{1/2}$, volume of distribution in liters, and CL of MGD014 are 10-12.5 days, 11-22 L, and 0.04 L/hr, respectively.

There were no increases in serum cytokine (IFN- γ , TNF- α , interleukin [IL]-2, IL-5, IL-6, or IL-10) concentrations or increases in activation markers (CD25, CD69, CD134, or CD137) on circulating CD4 $^{+}$ or CD8 $^{+}$ T cells following MGD014 administration. Most circulating CD4 $^{+}$ or CD8 $^{+}$ T cells exhibited MGD014 binding at 24 hours following MGD014 administration at 100 or 300 mcg/kg.

2.3.2.2 MGD014 Non-Clinical Experience

Non-clinical studies necessary to support clinical studies with MGD014 have been performed and are summarized in the **MGD014 IB**.

2.4 Dose Selection

2.4.1 MGD020 Dose Selection

A first-in-human starting dose of 1 mcg/kg MGD020 is proposed. Rationale supporting this dose selection is based on nonclinical data with MGD020 and nonclinical and clinical data with MGD014. MGD014 is a DART molecule with a structure like MGD020 but with specificity for a different HIV-1 env epitope. The MGD020 MABEL of 7 ng/mL corresponds to the median EC₅₀ for in vitro redirected T-cell cytotoxicity of human CD4⁺ cells infected by HIV-1 IMCs. An MGD020 starting dose of 1 mcg/kg is projected to yield a C_{max} of ~24 ng/mL, which exceeds the MABEL by ~3-fold. The 1 mcg/kg dose is expected to be a safe starting dose for MGD020 based on the rarity of target cells (HIV-1-infected, env-expressing cells) in PWH on ART, and thus the risk of adverse effects due to cytokine release or T-cell activation resulting from MGD020-mediated activity is minimal. The starting dose is supported by a study conducted in SHIV-infected rhesus monkeys on ART in which MGD020 was well tolerated when administered at 1 mg/kg weekly for 6 weeks. The 1 mg/kg dose yielded mean C_{max} of 27,200 ng/mL with no increases in serum cytokines or activation of circulating T cells. The starting dose is also supported by clinical experience with MGD014. MGD014 was well tolerated in Study CP-MGD014-01 conducted in PWH on ART when administered at doses ranging from 0.1 to 300 mcg/kg with mean C_{max} of 23.7 ng/mL at 1 mcg/kg and 5108 ng/mL at 300 mcg/kg. No DLT or SAEs were observed. There were no increases in serum cytokines or activation of circulating T cells following MGD014 administration at all dose levels examined.

2.4.1.1 Rationale for Every 2 Week Administration

Part 2 uses multi-dose, sequential administration of the combination of a fixed dose of MGD020 and a fixed dose of MGD014 on a Q2W schedule. The Q2W dosing is based on simulation of PK data of the MGD014 dose escalation part of Study CP-MGD014-01. Because the PK of MGD020 and MGD014 were comparable in a study conducted in SHIV-infected rhesus monkeys on ART, PK of both MGD020 and MGD014 DART molecules is expected to be comparable in PWH on ART.

2.4.2 MGD020 and MGD014 Combination Dose Selection

In Part 1B, a single ascending dose of MGD020 will be combined with a fixed dose of MGD014. The 300 mcg/kg dose of MGD014 was selected on the basis of non-clinical studies and available clinical data from Study CP-MGD014-01 (see **Section 2.3.2.1**). In Study CP-MGD014-01, doses ranging from 0.1 to 300 mcg/kg were examined in the single ascending dose part of the study. MGD014 was well tolerated with no observed DLTs, SAEs, or treatment-related AEs leading to study drug discontinuation. A dose of 300 mcg/kg was selected for evaluation in the multiple-

ascending dose part of Study CP-MGD014-01, where MGD014 is administered by IV infusion Q2W for a total of 3 infusions over 4 weeks.

In Part 1B, the starting dose of MGD020 is the dose determined to be one dose level lower than the MTD/MAD determined in Part 1A. A dose de-escalation design is employed.

In Part 2, the MGD020 dose will be the MTD/MAD from Part 1B combined with 300 mcg/kg MGD014.

2.4.3 Post-Infusion Monitoring

Events of infusion related reaction (IRR) including cytokine release syndrome (CRS) typically occur within the first hours (up to 24 hours) after infusion of a biologic. These events generally appear in the dose finding phase of studies (3, 15, 18, 19). No events of IRR or CRS have been observed in participants dosed with MGD014 in Study CP-MGD014-01 to date.

As a conservative measure, participants will be monitored on-site per **Section 6.5.1** following study drug infusion(s).

2.5 Risk Benefit Assessment

2.5.1 Risk Assessment

Details for information on risks of MGD020 and MGD014 are provided in their respective IBs.

One clinical study of MGD014 is ongoing (Study CP-MGD014-01) as described in **Section 2.3.2.1**. MGD014 infusions were well tolerated with no SAEs, DLTs, or increase in serum cytokine levels. No clinical studies of MGD020 have been conducted. It is expected MGD020 will have similar risks as MGD014, because MGD020 and MGD014 are based on the same DART molecule structure. Refer to the respective IBs for a summary of non-clinical information.

The combination of MGD020 and MGD014 is expected to have risks similar to administration of either study drug alone.

Infusion related reaction and CRS are potential risks of DART molecules. These risks typically occur within the first hours after infusion of the study drug. Management of CRS and IRR is based on the severity of reaction, including temporarily stopping the infusion, administering histamine blockers, corticosteroids, and resuming the infusion of study drug at a slower rate (see **Section 7.1**) (15, 18).

2.5.2 Benefit Assessment

The addition of MGD020 as a single agent or in combination with MGD014 to a participant's ART regimen provides no direct benefit to participants. Participation contributes to ongoing HIV-1 research, potentially resulting in the development of new treatments for HIV-1 infection.

2.5.3 Overall Assessment

The protocol incorporates risk mitigation measures including eligibility criteria, monitoring of participants, and discontinuation criteria. An independent safety monitor will provide study oversight and evaluate cumulative safety and other clinical data at regular intervals. Anticipated AEs are expected to be managed using standard of care. The risk-benefit profile supports investigation of MGD020 as a single agent or in combination with MGD014 in the study population.

3 STUDY OBJECTIVES

3.1 Primary Objective

Primary Objective	Outcome or Endpoint
Characterize safety and tolerability of MGD020 as a single agent and in combination with MGD014	1. Incidence of treatment-emergent AEs, SAEs, and AEs leading to discontinuation

Abbreviations: AE: adverse event; SAE: serious adverse event.

3.2 Secondary Objectives

Secondary Objective	Outcome or Endpoint
Assess PK and immunogenicity (ADA) of MGD020	1. Serum MGD020 concentrations 2. Summary PK parameters for MGD020 3. Incidence of ADA to MGD020
Assess PK and immunogenicity (ADA) of MGD014	1. Serum MGD014 concentrations 2. Summary PK parameters for MGD014 3. Incidence of ADA to MGD014
Assess serum cytokine levels	1. Serum cytokine concentrations

Abbreviations: ADA: anti-drug antibody; PK: pharmacokinetics.

3.3 Exploratory Objectives

Results of exploratory objectives may not be included in the clinical study report (CSR) unless they represent meaningful findings.

Exploratory Objective	Outcome or Endpoint
Explore T-cell binding	1. Percentages of peripheral CD4 and CD8 T cells with study drug bound over time
Explore immunologic responses	1. Changes in markers of activation or exhaustion on peripheral CD4 and CD8 T cells over time
Explore markers of persistent HIV-1	1. Changes in frequency of resting CD4+ T-cell infection by QVOA and/or IPDA 2. Changes in levels of rca-RNA 3. Changes in levels of residual low-level HIV-1 viremia quantified by SCA
Explore correlations between virologic and immunologic markers	1. Association between changes in immunologic and virologic markers

Abbreviations: CD: cluster of differentiation; HIV-1: human immunodeficiency virus-1; IPDA: intact proviral DNA assay; QVOA: quantitative viral outgrowth assay; rca-RNA: resting CD4+ T-cell-associated HIV-1 gag RNA; RNA: ribonucleic acid; SCA: single copy assay.

4 STUDY DESIGN

4.1 Overall Study Design

Study CP-MGD020-01 is a phase 1, open-label, dose-escalation, and multi-dose expansion study of MGD020 as a single agent or in combination with MGD014 in PWH on ART. The study is designed to characterize the safety, tolerability, PK, immunogenicity, and PD of the study drugs. The study consists of 3 parts (Part 1A, Part 1B, and Part 2). In all parts, the participant's standard of care ART regimen is continued throughout the study period.

Part 1A evaluates single ascending doses of MGD020, Part 1B evaluates single ascending doses of MGD020 in combination with fixed-dose MGD014, and Part 2 is a multi-dose expansion cohort with sequential administration of combination MGD020 and MGD014 Q2W for 3 combination doses over 4 weeks.

The study consists of a screening phase of up to 8 weeks, and an approximately 6-week (Part 1A and Part 1B) or 11-week (Part 2) study period (dosing and follow-up), which concludes with an end of study visit (EOSV) approximately 6 weeks (Part 1A and Part 1B) or 7 weeks (Part 2) after the last dose of study drug. Thus, the total study duration for each participant is approximately 14 weeks (Part 1A and Part 1B) or 19 weeks (Part 2). If a participant is unable to complete the study, but has not withdrawn consent, the EOSV is conducted 30 days (+3 day window) after the last dose of study drug.

An independent safety monitor will provide study oversight and evaluate cumulative safety and other clinical data at regular intervals as described in [Section 14.9](#).

4.1.1 Part 1A: Single Ascending Dose of MGD020

Part 1A evaluates single ascending doses of MGD020 with a 1+3 design for cohorts 1–3 and a 3+3 design for cohorts 4–6. A 2-week DLT period is observed prior to escalation to the next cohort level.

Part 1A has 6 cohorts ([Table 1](#)). For cohorts 1–3, each cohort consists of 1 participant, unless a DLT occurs, which prompts expansion of the cohort to add an additional 3 participants. For cohorts 4–6, each cohort consists of 3 participants, with at least 24 hours between dosing of each participant within the cohort. If a DLT is experienced in 1 of the 3 participants in the cohort, the cohort will be expanded to add 3 additional participants. If one or more of the additional 3 participants treated at any given dose level also experiences a DLT, then that dose level will be defined as exceeding the MTD. The MTD will then be defined as the next lower dose level of MGD020. Escalation proceeds according to the rules described in [Section 4.2](#) until either the MTD or MAD is determined.

Table 1 **MGD020 Dose Escalation Scheme (Part 1A)**

Cohort	MGD020 Dose (mcg/kg)	Design
1	1	1+3
2	3	1+3
3	10	1+3
4	30	3+3
5	100	3+3
6	300	3+3

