4.2 Dose Escalation Rules

Dose escalation from one dose cohort to the next higher dose cohort depends upon the clinical safety profile (e.g., evaluation of AEs, vital signs, ECGs, and clinical laboratory parameters) of the dose administered up to and including the preceding dose cohort. Dose escalation to the next dose level is permitted only after the participants enrolled in the current dose cohort have completed the DLT evaluation period and the safety data have been reviewed by the sponsor medical monitor and the study investigators. Evaluation of safety data from each cohort will include an assessment of the proportion of participants who receive planned doses, and the percentage of participants that require dose reductions or dose discontinuations for toxicity. Available data from participants both during and beyond the 2-week DLT evaluation period will be considered when making dose escalation decisions.

Dose escalation continues until all cohorts are enrolled, provided the MTD is not exceeded. If 2 or more of the participants in a dose cohort experience a DLT, the MTD will have been exceeded. If a DLT occurs in 1 participant in a dose cohort, the dose cohort will be expanded to an additional 3 participants. Prior to dosing any additional participants at the same dose, study drug safety and tolerability are evaluated over the entire 2-week DLT period for the first additional participant.

If the first additional participant does not experience a DLT during the DLT period, the 2 other additional participants can proceed to receive study drug at this dose with a minimum of 24 hours between dosing of each participant. If none of the 3 additional participants experience a DLT during the DLT period, dose escalation to the next dose cohort may proceed.

If any of the 3 additional participants experiences a DLT during the DLT period (≥ 2 DLTs within the same dose cohort), no further participants will receive a dose at this dose level, as the MTD will have been exceeded. Part 1B then proceeds at one dose level below the single-agent MTD_{1A}/MAD_{1A} of MGD020 determined in Part 1A. If only 1 participant was enrolled at the prior dose level in Part 1A, an additional 3 participants will be enrolled at the prior dose for evaluation of the MTD/MAD.

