4.3 Dose-Limiting Toxicity

DLT is defined based on treatment-related AEs that occur during the DLT period following study drug administration. The DLT period is defined as the period from initial infusion of study drug(s) through 2 weeks following the last study drug infusion.

Severity of AEs is graded according to the National Institute of Allergy and Infectious Diseases (NIAID) Division of Acquired Immunodeficiency Syndrome (DAIDS) Table for Grading the Severity of Adult and Pediatric Adverse Events, corrected version 2.1, July 2017 (see [Section 12.1.6](#)).

A DLT is any \geq Grade 2 treatment-related AE, with the following exceptions, based on the medical judgement of the investigator (or designee) and medical monitor:

- Grade 2 laboratory abnormality that lasts $<$ 72 hours and is not otherwise associated with clinical complications.
- Grade 2 fatigue that lasts $<$ 7 days.

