14.9 Cohort Analyses and Monitoring

As described in **Section 4.2**, the decision to escalate doses from cohort to cohort will only occur based on consensus supporting escalation by the investigator (or designee) and medical monitor. The review will include aggregate safety data through the DLT period for all dosed participants from the prior dose cohort.

An independent safety monitor will receive monthly study progress and safety monitoring reports. Study feasibility and the achievement of study milestones will be assessed in these reports. Additionally, accrual, baseline characteristics, conduct of the study (including premature study discontinuations), any interruptions of ART, virologic failures, and all reported toxicities and events will be monitored during the study on a monthly basis. Safety data will be reviewed to assess the relationship of reported toxicities and AEs to study drug(s).

If at any time during the study, 2 or more participants (in any part of the study) experience a toxicity that is Grade 3 or higher and considered related to study drug (per investigator assessment) or 2 or more participants experience the same toxicity that is Grade 2 or higher and considered related to study drug (per investigator) then enrollment and further dosing of ongoing participants will be suspended and the independent safety monitor will be asked to review all safety data, review study drug attribution to the event(s), and recommend how the study should proceed with respect to resuming enrollment and continuing study drug.

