Appendix 1 Time and Events Schedules

Table 7 Time and Events Schedule (Part 1A and Part 1B)

Procedure	Screening ^a	Dosing	Follow-up Period							End of Study ^b
			1	2	3	4	5	6	7	
Visit	Screen	1								8
Study Day	Day -56 to -1	Day 1	Day 2	Day 3	Day 8 (± 2 days)	Day 15 (± 2 days)	Day 22 (± 2 days)	Day 29 (± 2 days)	Day 43 (± 3 days)	
Study Drug Administration										
MGD020 infusion (Part 1A and Part 1B) ^c		X								
MGD014 infusion (Part 1B only)		X								
Clinical Procedures										
Informed consent	X									
Inclusion/exclusion criteria	X									
Enrollment	X									
Medical history	X									
Demographics	X									
Physical examination ^d	X	X	X	X	X	X	X	X	X	
Vital signs ^e	X	X	X	X	X	X	X	X	X	
Weight	X	X								
Height	X									
ART adherence	X	X	X	X	X	X	X	X	X	
Concomitant medications	X	X	X	X	X	X	X	X	X	
ECG ^f	X	X								X
Adverse events ^g	X	X	X	X	X	X	X	X	X	
Clinical Laboratory Collection ^h										
Hematology	X	X ⁱ	X		X		X		X	
Chemistry	X	X ⁱ	X		X		X		X	
Coagulation	X									X
Urinalysis	X									X
Pregnancy test ^j	X	X ^j							X	X
Optional FSH	X									
CD4/CD8	X									X
HIV-1 PCR viral load	X									X

Table 7 Time and Events Schedule (Part 1A and Part 1B)

Procedure	Screening ^a	Dosing	Follow-up Period							End of Study ^b
			1	2	3	4	5	6	7	
Visit	Screen	Day 1	Day 2	Day 3	Day 8 (± 2 days)	Day 15 (± 2 days)	Day 22 (± 2 days)	Day 29 (± 2 days)	Day 43 (± 3 days)	
Study Day	Day -56 to -1									
Rapid plasma reagin	X									
Hepatitis B surface antigen	X									
HCV antibody or RNA ^k	X									
Research Laboratory Sample Collection										
PK/ADA/PD/cytokines/HLA	See Table 9 (Part 1A) or Table 10 (Part 1B) in Appendix 2									

- a Results of standard-of-care tests or examinations performed prior to obtaining informed consent and within the 56 day window may be used for screening.
- b If a participant is unable to complete the study, but has not withdrawn consent, the end of study visit (EOSV) is conducted 30 days (+3 day window) after the last dose of study drug(s).
- c MGD020 is infused first on days when both MGD020 and MGD014 are administered (Part 1B only).
- d Full physical exams are performed at screening and EOSV. All other physical exams are directed physical exams based on signs and symptoms, and as clinically indicated.

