- e At the dosing visit, vital signs are measured pre-infusion; at 15 and 30 min after start of infusion (± 5 min); at end of infusion (EOI) of all study drug(s) (± 5 min); at 15, 30, 45, and 60 min post-infusion of last study drug (± 5 min); then every 60 min (± 10 min) until 6 hours after EOI or until the end of the monitoring period (see [Section 6.5.1](#)), whichever comes first. For participants on Parts 1A and 1B, vital signs are also measured at 10 hours (± 10 min) after the EOI. At non-dosing in-person visits, vital signs are assessed once.
- f ECGs are performed in triplicate (approximately 1 min apart). At screening and EOSV, ECGs will be taken at one time point. At the dosing visit (Day 1), ECG is recorded pre-infusion, at EOI of all study drug(s), at 30 and 60 min after EOI of last study drug, and as clinically indicated. ECGs after EOI have a ± 10 min window.
- g Assess participants for adverse events. Participants are also instructed to contact the study coordinator or investigator if any signs or symptoms of an AE occur at any time during the study.
- h Additional and/or more frequent safety laboratory tests may be performed as clinically indicated per the investigator's discretion.
- i Clinical laboratory assessments scheduled for Day 1 can be obtained within 7 days prior to infusion. See [Section 9.11](#) for detailed list of assessments. Indirect bilirubin is required if participant on atazanavir.
- j Participants of childbearing potential only. Serum pregnancy test is required at screening. Subsequent pregnancy tests may use serum or urine. Results must be reviewed before study drug infusion. If screening test is performed within 72 hours of study drug infusion, repeat testing on Day 1 may be deferred.
- k Reflex HCV PCR viral load test is performed only if positive for HCV antibody.

Abbreviations: ADA: anti-drug antibody; ART: antiretroviral therapy; CD: cluster of differentiation; ECG: electrocardiogram; EOI: end of infusion; EOSV: end of study visit; FSH: follicle stimulating hormone; HCV: hepatitis C virus; HIV-1: human immunodeficiency virus-1; HLA: human leukocyte antigen; PCR: polymerase chain reaction; PD: pharmacodynamics; PK: pharmacokinetics.

Table 8 Time and Events Schedule (Part 2)

Procedure	Screening ^a	Dosing Period						Follow-up Period			End of Study ^b
		1	2	3	4	5	6	7	8	9	

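### Parts 1A and 1B: Table 7 appears to schedule no hematology or chemistry after Day 8 within the 14-day DLT period; add both to the existing Day 15 draw once the table is confirmed

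*Protocol*

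**What the plan says.** **DLT period.** Protocol section 4.1.1: "A 2-week DLT period is observed prior to escalation to the next cohort level". Section 4.3: "The DLT period is defined as the period from initial infusion of study drug(s) through 2 weeks following the last study drug infusion". A DLT is a treatment-related AE of Grade 2 or higher. Among laboratory findings, the only exception is a Grade 2 abnormality that lasts under 72 hours without clinical complications.

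**Escalation.** Section 4.2 says escalation "depends upon the clinical safety profile (e.g., evaluation of AEs, vital signs, ECGs, and clinical laboratory parameters"), and it requires a completed DLT period and a safety review. It adds: "Available data from participants both during and beyond the 2-week DLT evaluation period will be considered when making dose escalation decisions". Section 14.9 says: "The review will include aggregate safety data through the DLT period for all dosed participants from the prior dose cohort".

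**Expansion.** After one DLT, the first additional participant is followed for the full DLT period. If no DLT occurs, "the 2 other additional participants can proceed to receive study drug at this dose with a minimum of 24 hours between dosing". Section 4.1.2 sets 72 hours between participants within a Part 1B cohort.

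**Schedule.** Table 7 (Appendix 1) covers Parts 1A and 1B. Its hematology and chemistry rows, read against its own Study Day row, are marked at screening and Days 1, 2, 8, 22 and 43. The Day 15 visit has a physical examination, vital signs, AE review and concomitant medications. Tables 9 and 10 draw blood that day for PK and ADA. Footnote h says: "Additional and/or more frequent safety laboratory tests may be performed as clinically indicated", at the investigator's discretion.

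**The concern.** DLT counts drive every escalation step and the MTD or MAD. A laboratory abnormality can be a DLT, and one without symptoms is found only by a test. If the last scheduled test before the decision is on Day 8, such an event in the second week would first be seen by schedule on Day 22. Section 4.2 does not require anyone to wait for that result.

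Expansion is the sharpest case. The dose has already caused one DLT, and the first additional participant serves as a sentinel for the other two. A silent laboratory DLT in that participant would be the second at that dose, and section 4.2 would then treat the MTD as exceeded and stop dosing there. The last 2 participants might already have been dosed.

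**Working it through.** **1. Day convention.** Section 4.1 places the end of study visit about 6 weeks after the dose, and Table 7 places it on Day 43: (43 − 1)/7 = 6.0 weeks, which agrees. On the same convention the DLT period closes on Day 1 + 14 = Day 15.

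**2. Reading Table 7.** Each extracted row has 10 cells for 9 visits, so alignment has to be checked.
- The Study Day row and the physical examination row fill cells 1 to 9. Footnote d says "Full physical exams are performed at screening and EOSV", so the ninth examination mark must be end of study.
- Hematology and chemistry are marked in cells 1, 2, 3, 5, 7 and 9, which gives screening and Days 1, 2, 8, 22 and 43.
- Pointing the other way, the End of Study header and six rows (ECG, coagulation, urinalysis, pregnancy, CD4/CD8, viral load) end in cell 10.
- Suppose end of study is cell 10 and one blank cell (4, 6 or 8) is spurious. Day 15 gains a test in two of the three cases (4 and 6), but Day 43 loses its test in all three. That is unlikely: other laboratory tests are marked at end of study, and Table 8 schedules both panels there in Part 2.

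**3. Coverage.** Days without a scheduled test = 15 − day of the last test.

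| Day 8 visit held on | Uncovered days | Share of 14 |
|---|---|---|
| 6 | 15 − 6 = 9 | 64% |
| 8 | 15 − 8 = 7 | 50% |
| 10 | 15 − 10 = 5 | 36% |

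The next scheduled test, Day 22 (20 to 24), comes 7 (5 to 9) days after close. Counting the period as Days 1 to 14 would give 6 (4 to 8) uncovered days, but section 4.3 supports the Day 15 close.

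**4. Expansion.** Let r be the days from DLT close to the next dose. The documents give no value, so r is an assumption. The first additional participant is dosed on day 1, reaches close on day 15 and has the next test on day 22.
- Part 1A, 24-hour spacing: next doses on days 15 + r and 16 + r. Both precede the test if 16 + r < 22, so r ≤ 5 (r ≤ 3 if drawn on Day 20, r ≤ 7 if on Day 24).
- Part 1B, 72-hour spacing: next doses on days 15 + r and 18 + r. Both precede the test if 18 + r < 22, so r ≤ 3 (r ≤ 1; r ≤ 5).

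**5. Escalation without expansion.** Exposure is counted to each participant's own Day 22 test, at minimum spacing, with r counted from the last participant's close.

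| Step | Participant | Own Day 22 test (calendar day) | Next-cohort doses (calendar day) | Doses that precede the test |
|---|---|---|---|---|
| 1A, 1→2 and 2→3 | the only one | 22 | 15+r | the 1 dose if r ≤ 6 |
| 1A, 3→4 | the only one | 22 | 15+r, 16+r, 17+r | all 3 if r ≤ 4 |
| 1A, 4→5 and 5→6 | first (dosed day 1) | 22 | 17+r, 18+r, 19+r | all 3 if r ≤ 2 |
| 1A, 4→5 and 5→6 | third (dosed day 3) | 24 | 17+r, 18+r, 19+r | all 3 if r ≤ 4 |
| 1B | first (dosed day 1) | 22 | 21+r, 24+r, 27+r | first only, if r = 0 |
| 1B | third (dosed day 7) | 28 | 21+r, 24+r, 27+r | first if r ≤ 6; all 3 if r = 0 |

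A Day 22 visit held 2 days early or late moves each limit by 2.

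**6. With a Day 15 test.** Drawn on Day 13, 15 or 17, it leaves 2, 0 or 0 days uncovered. A new uncomplicated Grade 2 value on Day 15 cannot yet be classed as a DLT because of the 72-hour exception. That status stays open until about Day 15 + 3 = Day 18.

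**The case against.** **The table is damaged.** The End of Study header sits in the tenth cell, and some rows follow it. This stands as a condition: the sponsor must check the source table first. It does not reverse the reading, because any one-cell shift that creates a Day 15 test removes the end of study tests.

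**A reader might infer that the protocol contradicts itself by promising laboratory data through DLT close.** The documents do not support that. Section 14.9 speaks only of aggregate safety data. The list in 4.2 is given as examples and includes ECGs, which Table 7 schedules only at screening, Day 1 and end of study. The list therefore cannot mean that every item is measured up to close.

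**A reader might also infer that Day 15 is unmonitored, or that participants face a known late hazard.** Neither follows. Clinical assessment is scheduled that day, extra tests are allowed, and section 14.9 has consensus review and a suspension rule. The evidence points to early onset: MGD014-related events were Grade 1 and fell on the infusion day (2.3.2.1), infusion reactions typically occur within 24 hours (2.4.3), and monkeys given 1 mg/kg weekly for 6 weeks showed no drug-related hematology changes (2.3.1.2.2). On the other side, MGD020 has no human data (2.3.1.1). Its PK is expected to resemble that of MGD014 (2.4.1.1), whose half-life is 10 to 12.5 days, so exposure would continue into the second week.

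These safeguards narrow the gap without closing it. Discretionary tests need a clinical prompt, later data count only if available, and the suspension rule acts on events already detected.

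**Conclusion.** The point holds as a gap in scheduled coverage, subject to confirming Table 7. On the extracted table, 7 of 14 days (range 5 to 9) before DLT close have no scheduled hematology or chemistry, and nothing requires a later test before escalation or before the last 2 expansion participants are dosed. The gap is confined to a silent, related laboratory abnormality that arises after the Day 8 draw.

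The documents give no rate for such events and no review time, so the day limits show what the schedule allows, not how likely harm is. The expansion limits (5 days or less in Part 1A, 3 or less in Part 1B) are the clearest consequence. This is a cheap improvement to DLT ascertainment, and it does not show that the escalation design is unsafe.

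**What to change.** 1. Confirm the hematology and chemistry rows of Table 7 against the source table. If Day 15 is already marked, only the section 4.2 wording below is needed.
2. Otherwise add both panels at Day 15 for Parts 1A and 1B, on the blood draw already planned for PK and ADA, and keep Day 22. Part 2 already schedules both panels on its Day 15 visit, although that is a dosing day.
3. State in section 4.2 that each participant's Day 15 AE and laboratory results are reviewed before escalation, and that those of the first additional participant are reviewed before the 2 remaining expansion participants are dosed.
4. State there that a new Grade 2 laboratory value on Day 15 is repeated at about 72 hours and that dosing waits for the result.
5. Optional: change the Day 15 window to 0/+2 days in Tables 7, 9 and 10, which removes the 2 days left uncovered by a Day 13 draw.

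**Cost.** A protocol amendment to two table cells and a short addition to section 4.2, with no new visit or venipuncture. Each participant gives a few extra tubes for local tests. Dosing decisions wait briefly for results: up to about 2 days when the visit falls on Day 16 or 17, and about 3 more when a new Grade 2 value must be repeated.
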